6. STUDY ENDPOINT

The primary efficacy endpoint is the proportion of patients in each treatment group with Therapeutic Cure (parasitological cure plus clinical cure) of scabies at the test-of-cure visit

**NOVUM PHARMACEUTICAL RESEARCH SERVICES
STATISTICAL ANALYSIS PLAN**

Permethrin Cream, 5%

Protocol / Study No. 71675502

conducted at Day 28 ± 4. A parasitological cure is defined as failure to demonstrate microscopically the presence of scabies infestation (i.e., no living mites, no viable mite eggs, and no mite fecal matter present). A clinical cure is defined as visual evidence of absence of new lesions and healing of original lesions, regardless the presence of post-scabietic nodules (i.e., post-scabietic nodules need not be considered as new lesions or persistence of old lesions).

Patients who do not respond to the initial treatment and have new lesions or microscopic confirmation of mites, ova, or fecal matter on Day 14 ± 4 will be treated as treatment failure in the final analysis on Day 28.

7. STUDY POPULATIONS

Per-Protocol (PP) Population

The PP population will include:

- Met the inclusion/exclusion criteria as defined in this protocol at Visit 1.
- Did not take any prohibited medications throughout the study.
- Did not have any significant deviations from the protocol. Did not develop any concurrent dermatological condition or illness exhibiting symptoms similar to scabies, or symptoms that in the Investigator's opinion would interfere with endpoint assessments.
- Completed the last study visit (Visit 3) Day 28 ± 4.

Patients will be included in the PP population as treatment failures in the final analysis on Day 28 (provided they had no significant protocol deviations) if they 1) withdrew from the study because of lack of efficacy, 2) show therapeutic cure at Day 14 ± 4 but re-infestation at Day 28 ± 4, or 3) do not respond to the initial treatment and have new lesions or microscopic confirmation of mites, ova, or fecal matter on Day 14 ± 4.

Safety Population

The safety population will include all patients who are randomized who applied at least one dose of the assigned study product.

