### 10.3.3 Restrictions During the Study

Patients will be instructed to refrain from the following treatments throughout the study:

- Any other prescription/over-the-counter (OTC)/natural/herbal scabicides.
- Systemic and topical corticosteroids or immunosuppressants (e.g., high dose of systemic corticosteroids, systemic calcineurin inhibitors, Azathioprine).
- Prolonged exposure to sunlight/UV, use of tanning beds, chemical treatments/peels, dermabrasion or any dermatological procedures that will potentially influence or hinder the evaluation of scabies signs and symptoms.

Note: Use of antibiotics (systemic and topical) for cutaneous bacterial infections during the conduct of the study will be allowed after the Screening/Baseline visit, but the usage should be restricted to the Principal Investigator's discretion in cases of secondary infections of scabietic lesions. The usage of the antibiotic should be included on the concomitant medication page.

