## CONFIDENTIAL PROTOCOL

A Randomized, Double-Blind, Parallel-Design, Multiple-Site Study to Evaluate the Therapeutic Equivalence of Permethrin Cream, 5% (Encube Ethicals) Compared to Elimite™ Cream (permethrin) 5% (Prestium Pharma, Inc.) in the Treatment of Scabies

---

- Significant AE that led the Investigator or patient to withdraw for safety reasons
- Non-compliance with protocol including the use of restricted medication
- Pregnancy
- Significant worsening of scabies such that the Investigator and/or patient believes it is in the best interest of the patient to withdraw from the study and be provided alternative treatment
- Participant enrolls in another clinical trial, or is found to have previously enrolled in this study

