### 11.8 Safety Analysis

Adverse events will be classified using standard MedDRA terminology Version 20.0 or higher and summarized by treatment group. Summary tables comparing the type, incidence, date of onset, date of resolution, severity, action taken, outcome and Investigator's opinion of relationship to the study product will be prepared by treatment group. If sufficient data exist, AE frequencies will be compared between treatments using Fisher's exact test or a similar test in the Safety population.

Signs and symptoms of scabies will not be considered AEs, unless in the Investigator's opinion, they have increased in frequency and/or severity to such an extent that the Investigator/patient considers that it is in the patient's best interest to be dropped from continued participation in the study and given alternative therapy for their condition.

Concomitant medication use during the study will be tabulated by patient.

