5. SAMPLE SIZE

For the primary endpoint analysis (proportion of patients in the PP population who are considered to be a Therapeutic Cure on Day 28 ± 4), sample size is estimated for therapeutic equivalence of the Test to the Reference product.

Based on data from a previous bioequivalence study conducted to support approval of the first generic product of permethrin cream, 5%, the therapeutic cure rate (p_R) of the Reference product (Elimite™ permethrin cream 5%) is expected to be about 88% in the PP population. Assuming that the Therapeutic Cure rate for the Test group (p_T) is an absolute difference of 5% lower than the Reference group (i.e., $p_T - p_R = -5\%$), a sample size of 107 patients in each active group in PP population will provide at least 90% power to demonstrate therapeutic equivalence (i.e., the 90% confidence interval [Yates' continuity corrected] on $p_T - p_R$ is within a defined equivalence range [-20%, +20%]).

To allow for approximately 14 % of patients who may drop out from the study or are otherwise non-evaluable, approximately 250 patients (125 in each treatment group) will be randomized, such that there will be an estimated 214 patients (107 per group) in the PP population for statistical evaluation of therapeutic equivalence.

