8.2 Efficacy Analyses

8.2.1 Primary Efficacy Analysis

Bioequivalence with Clinical Endpoints Analysis

The proportion of patients in each treatment group with Therapeutic Cure is the primary efficacy endpoint of the study.

The Per Protocol (PP) Population will be used for the analysis of equivalence.

Based on the usual method used in OGD for binary outcomes, the 90% confidence interval for the difference in success proportions between test and reference treatment should be contained within [-0.20, +0.20] (or [-20%, +20%] in percent) in order to establish equivalence.

The compound hypothesis to be tested is:

$$H_0: P_T - P_R < -20\% \text{ or } P_T - P_R > 20\% \quad \text{versus}$$

$$H_A: -20\% \leq P_T - P_R \leq 20\%$$

**NOVUM PHARMACEUTICAL RESEARCH SERVICES
STATISTICAL ANALYSIS PLAN**

Permethrin Cream, 5%

Protocol / Study No. 71675502

where P_T = percent cure rate of test treatment
 P_R = percent cure rate of reference treatment.

Let

n_T = sample size of test treatment group
 cn_T = number of cured patients in test treatment group
 n_R = sample size of reference treatment group
 cn_R = number of cured patients in reference treatment group

$$\hat{P}_T = cn_T/n_T \quad \hat{P}_R = cn_R/n_R, \quad \text{and}$$

$$se = (\hat{P}_T (1 - \hat{P}_T)/n_T + (\hat{P}_R (1 - \hat{P}_R)/n_R)^{1/2}$$

where \hat{P}_T = estimated cure rate (%) of test treatment
 \hat{P}_R = estimated cure rate (%) of reference treatment.

The 90% confidence interval for the absolute difference between the proportions of patients in test and reference who are considered a therapeutic cure (primary) will be calculated as follows:

$$L = (\hat{P}_T - \hat{P}_R) - 1.645 se$$

$$U = (\hat{P}_T - \hat{P}_R) + 1.645 se$$

If the 90% confidence interval⁰ for the absolute difference between the proportion of patients who are considered a therapeutic cure (primary) in the Test and Reference groups is contained within the range [-20% + 20%] then bioequivalence of the Test product to the Reference product will be considered to have been demonstrated for the primary endpoint.

Sensitivity Analysis for Primary Efficacy Endpoint

As a sensitivity analysis, the primary efficacy analysis will be performed on the safety population using LOCF. This analysis will use LOCF such that subjects with no post-dose data will be considered as non-responders.

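### Use of another scabicide for the patient's own scabies, and possibly withdrawal for worsening, removes treatment failures from the primary per-protocol analysis

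*SAP*

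**What the plan says.** - Protocol 10.3.3 lists among the treatments patients must avoid: "Any other prescription/over-the-counter (OTC)/natural/herbal scabicides".
- SAP 7 (same text in Protocol 11.3.1) makes it a condition of PP membership that the patient "Did not take any prohibited medications throughout the study". No exception is stated for use prompted by failure of the study product.
- The same section keeps three groups in PP as failures: those who "withdrew from the study because of lack of efficacy", those cured at Day 14 but re-infested at Day 28, and Day 14 non-responders. This applies only if they had no significant protocol deviation, and significant is not defined. The deviation table shell T14.1.2 has a row for restricted medication use.
- Protocol 10.3.4 lists as one removal reason "Non-compliance with protocol including the use of restricted medication". It lists significant worsening of scabies, with alternative treatment provided, as another, and a significant adverse event (AE) as a third.
- Protocol 11.8 makes scabies signs and symptoms an AE when they worsen so far that the patient should be "dropped from continued participation in the study and given alternative therapy for their condition". The disposition shell T14.1.1 has separate rows for adverse event and lack of efficacy.
- SAP 8.2.1 adds a sensitivity run on the Safety population with last observation carried forward (LOCF), in which "subjects with no post-dose data will be considered as non-responders". It has no rule for patients who used another scabicide.
- SAP 8.2.2 rests the equivalence decision on the primary PP analysis alone.

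**The concern.** Treating oneself again because the infestation persists or returns is an outcome of the study product. The plan handles it as a reason for exclusion. The patients removed are failures, and a product that fails more often will tend to lose more of them. If so, both PP cure rates rise, the worse arm's rises more, and the observed difference moves toward zero, which is the direction that helps an equivalence claim. The opportunity exists by design, since generic permethrin is offered to household members and close contacts who need treatment (Protocol 10.1, 10.4.1).

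At stake is the 5% limit on declaring equivalence for a product that is really 20 points worse.

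**Working it through.** **Step 1. Follow each kind of patient through the text.**

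| Patient | Primary PP analysis | Safety-population run |
|---|---|---|
| Clear at Visit 2, relapses, uses another scabicide, clear at Visit 3 | Excluded by the prohibited-medication criterion; none of the three failure groups fits | Has post-dose data and a clear Visit 3: can count as a cure |
| Same, but infested at Visit 3 | Fits the re-infestation group, but breaches the criterion, and the deviation proviso can block restoration | Failure |
| Day 14 failure who then uses another scabicide | Fits the Day 14 group, subject to the same proviso | Failure (SAP 6) |
| Withdrawn for worsening, recorded as lack of efficacy | Failure | Normally a failure, from the early-termination assessment |
| Withdrawn for worsening, recorded as AE, no Day 14 failure documented | No Visit 3 in window and not restored: excluded | Normally a failure, if that assessment was done |

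The first row follows directly from the text. The last depends on how the reason is coded.

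**Step 2. Reproduce the plan's own figure.** SAP 5 states that "a sample size of 107 patients in each active group in PP population will provide at least 90% power to demonstrate therapeutic equivalence", with 88% Reference, 83% Test, margin ±20 points and a Yates-corrected 90% interval.

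- se = √(0.83×0.17/107 + 0.88×0.12/107) = 0.0480
- Correction = (1/107 + 1/107)/2 = 0.0093
- z = (0.20 − 0.05 − 0.0093)/0.0480 − 1.645 = 1.28, so power is 90.0% (exact enumeration 89.8%)
- With the uncorrected interval of SAP 8.2.1, power is 93.0% (exact 92.9%)
- 107/0.86 = 124.4, so 125 per arm, leaving 125 − 107 = 18 per arm for all non-evaluable patients

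The stated design is reproduced.

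**Step 3. Effect of losing failures when Test is at the margin.** Assume true cure of 88% Reference and 68% Test, 107 per arm before removal, and the same fraction f of failures leaving PP in each arm. For true cure rate p:

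- PP cure rate = p / [p + (1 − p)(1 − f)]
- Expected number removed = 107 × (1 − p) × f

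For f = 10%: Test 0.68/(0.68 + 0.32×0.9) = 70.2%; Reference 0.88/(0.88 + 0.12×0.9) = 89.1%; difference −18.8 points. The chance of passing is the exact binomial probability that the uncorrected 90% interval lies within ±20 points.

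| f | PP difference (points) | Removed, Test / Reference | False equivalence |
|---|---|---|---|
| 0 | −20.0 | 0 / 0 | 5.1% |
| 5% | −19.4 | 1.7 / 0.6 | 6.6% |
| 10% | −18.8 | 3.4 / 1.3 | 8.0% |
| 25% | −16.8 | 8.6 / 3.2 | about 16% |

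These treat the number removed as fixed. Letting it vary at random moves the results by only a few tenths of a point.

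**Step 4. Direction.** With f = 25% in Test only, false equivalence is 29.5%. With f = 25% in Reference only, it falls to 1.7%.

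As a worked example, suppose the PP result is 89/107 v 94/107: difference −4.7 points, 90% interval −12.6 to +3.2, a pass. Putting excluded failures back gives:

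- 4 Test, 0 Reference: −15.8 to +0.4
- 8 Test, 0 Reference: −18.7 to −2.2
- 10 Test, 0 Reference: −20.1 to −3.5, a fail
- 8 Test, 8 Reference: −13.1 to +4.4, almost unchanged

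Ten is within the allowance of 18 per arm, but here all ten come from one arm.

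**The case against.** Four points on the other side carry weight.

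**Worsening withdrawals are ambiguous, not certainly lost.** A reader might infer that everyone given alternative treatment leaves PP. The documents do not support that. Lack-of-efficacy withdrawals stay in as failures. Protocol 10.3.4 lists worsening separately from withdrawal for a safety AE, and lack of efficacy is the natural row for it in T14.1.1. Protocol 11.8 says when worsening is reported as an AE, not that the withdrawal reason becomes AE. The shells are also described as a general layout. What remains is a missing sentence that maps worsening to failure.

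**Large values of f are hard to reach.** Day 14 failures already count unless their scabicide use is judged a significant deviation, and Protocol 8.3 expects few re-infestations between Day 14 and Day 28. At f = 50% the calculation gives about 47%, but it needs 107 × 0.32 × 0.5 = 17 Test patients to leave this way, nearly the whole allowance of 18 for every cause. That figure should not be used.

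**The direction is conditional.** A reader might infer that the rule always favours equivalence. Step 4 shows that it does not.

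**The remedy can misclassify.** Protocol 10.4.1 says persistent itching is not a sign of treatment failure. Someone who reapplied a scabicide for itch alone would become a failure without microscopic or lesion evidence.

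These points limit the size and certainty of the effect. They do not touch the first row of Step 1, where the rule applied exactly as written removes a product failure from the deciding analysis and no other planned analysis is sure to count it.

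**Conclusion.** The concern holds in limited form. A patient who uses another scabicide for his or her own persistent or returning scabies before Visit 3 is excluded from PP instead of counted as a failure, and the Safety-population run can score that patient as a cure. A patient withdrawn for significant worsening can be lost as well, depending on the recorded reason.

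The bias runs toward equivalence when Test is truly worse and failures leave at similar rates in both arms, or when exclusions concentrate in the worse arm. Similar numbers leaving each arm change little, and losses mainly in Reference work against equivalence.

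On the Step 3 assumptions, the reasonable reading of the size is a rise in false equivalence from 5.1% to 6.6%–8.0% for f of 5% to 10%. The result at f = 25% is illustrative only, since the documents give no value for f. The effect may be small, but the gap lies in the one analysis that decides the trial, and it can be closed at little cost before lock.

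**What to change.** Change the analysis only, in SAP 6, 7 and 8.2.1 and in Protocol 11.3.1 and 11.5:

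- Count as a Therapeutic Failure, in both the PP and the Safety-population analyses, any patient who before Visit 3 used a non-study scabicide for his or her own persistent, recurrent or worsening scabies, and any patient withdrawn for worsening scabies, whatever reason code was recorded.
- Exempt that use from the prohibited-medication criterion and from the proviso on significant deviations. Other prohibited-medication use stays an exclusion.
- Classify these patients blind, before database lock, from the Indication column of listing L16.2.4.3 and the withdrawal records. SAP 4 releases the randomization schedule to the statistician only after lock, so this is feasible.
- Add a sensitivity run that omits those counted as failures under this rule who have neither microscopic evidence nor new lesions.

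The cost is wording, one blinded review and one extra table. Protocol 8.3 dates the last patient visit to October 30, 2017; the change needs no new data or patients, and the sample size is unaffected. The downside is that a few patients who re-treated for itch after a successful cure may count as failures, slightly lowering both cure rates. The added run shows how much that matters.

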### 10.4.6 Compliance

Patients will be provided with a diary to record the time and date of dosing, concomitant medications and AEs. Use of restricted medications will be reviewed based on patient diary entry(s) and verbal discussion with the patient. Dosing compliance will be checked based on the dosing diary entry and verbal discussion with the patient at Visits 2 and 3 (when applicable). Patients will be considered compliant with dosing if they administer 100% of the required number of doses (i.e., one or, if necessary, two doses).

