9. TABLE, LISTING AND FIGURE SHELLS

The following shells are provided in order to provide a framework for the display of data from this study. These shells may not be reflective of every aspect of this study but are intended to show the general layout of the Tables, Listings and Figures that will be included in the final clinical study report. Tables, Listings and Figures are numbered following the ICH structure. Table headers, variables names and footnotes will be modified as needed following data analyses. All descriptive and inferential statistical analyses will be performed using SAS[®] statistical software Version 9.4 or higher, unless otherwise noted.

TABLE, LISTING AND FIGURE SHELLS

Programming note:

Put Program Name in the footnote where it is stored, Location of Output stored, and Date and time when the output is generated.

T14.1.1 Summary of Patient's Disposition

Patients Randomized	Test N = xxx n (%)	Reference N = xxx n (%)	Total N = xxx n (%)
Completed Study	xxx (xx.x)	xxx (xx.x)	xxx (xx.x)
Terminated Early	xxx (xx.x)	xxx (xx.x)	xxx (xx.x)
Adverse Event	xxx (xx.x)	xxx (xx.x)	xxx (xx.x)
Lack of efficacy	xxx (xx.x)	xxx (xx.x)	xxx (xx.x)
Protocol Deviation	xxx (xx.x)	xxx (xx.x)	xxx (xx.x)
Pregnancy	xxx (xx.x)	xxx (xx.x)	xxx (xx.x)
etc.			
Other	xxx (xx.x)	xxx (xx.x)	xxx (xx.x)

Test: Permethrin Cream, 5%, (Encube Ethicals)

Reference: Elimate™ Cream (permethrin) 5% (Prestium Pharma, Inc.)

N= number of patients randomized in that particular group; n= number of patient with data available for that particular group;

total % is based on N

PROGRAM: L:\DEV\755\71675502\SAS\PGM\XXXX
 Created on: ddmmmyy hh:mm

OUTPUT: L:\DEV\755\71675502\SAS\OUT\XXXX
 Page 1 of N

T14.1.2 Summary of Protocol Deviations

	Test N = xxx n (%)	Reference N = xxx n (%)	Total N = xxx n (%)
Total Patients with Protocol Deviations	xxx (xx.x)	xxx (xx.x)	xxx (xx.x)
Total Deviations	xxx	xxx	xxx
Lost to Follow-up	xxx	xxx	xxx
Missed Visit	xxx	xxx	xxx
Non-compliance with dosing requirements	xxx	xxx	xxx
Outside Visit Window	xxx	xxx	xxx
Restricted Medication Use	xxx	xxx	xxx
Randomized in Error	xxx	xxx	xxx
Other	xxx	xxx	xxx

Test: Permethrin Cream, 5%, (Encube Ethicals)

Reference: Elimite™ Cream (permethrin) 5% (Prestium Pharma, Inc.)

N= number of patients randomized in that particular group; n= number of patient with data available for that particular group;
total % is based on N

PROGRAM: L:\DEV\755\71675502\SAS\PGM\XXXX
Created on: ddmmmyy hh:mm

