OUTPUT: L:\DEV\755\71675502\SAS\OUT\XXXX
Page 1 of N

**T14.1.3.1 Summary of Patients Excluded from Efficacy Analysis
(Population Determination)**

	Test N = xxx n (%)	Reference N = xxx n (%)	Total N = xxx n (%)
Safety Population	xxx (xx.x)	xxx (xx.x)	xxx (xx.x)
Excluded from Safety population	xxx (xx.x)	xxx (xx.x)	xxx (xx.x)
PP Population	xxx (xx.x)	xxx (xx.x)	xxx (xx.x)
Excluded from PP population	xxx (xx.x)	xxx (xx.x)	xxx (xx.x)
Inclusion/Exclusion criteria not met	xxx (xx.x)	xxx (xx.x)	xxx (xx.x)
Non-compliant with dosing requirement	xxx (xx.x)	xxx (xx.x)	xxx (xx.x)
Major protocol deviations	xxx (xx.x)	xxx (xx.x)	xxx (xx.x)
etc.	xxx (xx.x)	xxx (xx.x)	xxx (xx.x)
	xxx (xx.x)	xxx (xx.x)	xxx (xx.x)

Test: Permethrin Cream, 5%, (Encube Ethicals)

Reference: Elimite™ Cream (permethrin) 5% (Prestium Pharma, Inc.)

N= number of patients randomized in that particular group; n= number of patient with data available for that particular group;
total % is based on N

PROGRAM: L:\DEV\755\71675502\SAS\PGM\XXXX
Created on: ddmmmyy hh:mm

OUTPUT: L:\DEV\755\71675502\SAS\OUT\XXXX
Page 1 of N

T14.1.3.2 Summary of Patients Included in Analysis Population by Study Center

Site No.	Name	Total Randomized	PP			Safety		
			Test	Reference	Total	Test	Reference	Total
XX	XXXX	XXX	XXX	XXX	XXX	XXX	XXX	XXX
XX	XXXX	XXX	XXX	XXX	XXX	XXX	XXX	XXX

Test: Permethrin Cream, 5%, (Encube Ethicals)
 Reference: Elimite™ Cream (permethrin) 5% (Prestium Pharma, Inc.)

PROGRAM: L:\DEV\755\71675502\SAS\PGM\XXXX
 Created on: ddmmmyy hh:mm

OUTPUT: L:\DEV\755\71675502\SAS\OUT\XXXX
 Page 1 of N

T14.1.3.3 Study Timelines (Screened subjects)

	Trial Timelines
	Date
First Patient First Visit (FPFV)	mm-DDD-YYYY
Last Patient Last Visit (LPLV)	mm-DDD-YYYY
Trial Duration (Days)	xxx

Note: Trial Duration (Days) = (Date of LPLV - Date of FPFV) + 1

PROGRAM: L:\DEV\755\71675502\SAS\PGM\XXXX
Created on: ddmmmyy hh:mm

OUTPUT: L:\DEV\755\71675502\SAS\OUT\XXXX
Page 1 of N

**T14.1.4 Summary of Demographic Data and Baseline Characteristics
(Safety Population)**

		Test n = xxx n (%)	Reference n = xxx n (%)	Total N = xxx n (%)	P-value
Age (years)	n	xxx	xxx	xxx	x.xxxx
	Mean ± SD	xx.x ± xx.x	xx.x ± xx.x	xx.x ± xx.x	
	Median	xx.x	xx.x	xx.x	
	Range	xx.x - xx.x	xx.x - xx.x	xx.x - xx.x	
Age Groups	< 18	xxx (xx.x)	xxx (xx.x)	xxx (xx.x)	x.xxxx
	18 – 40	xxx (xx.x)	xxx (xx.x)	xxx (xx.x)	
	41 – 64	xxx (xx.x)	xxx (xx.x)	xxx (xx.x)	
	65 – 75	xxx (xx.x)	xxx (xx.x)	xxx (xx.x)	
	> 75	xxx (xx.x)	xxx (xx.x)	xxx (xx.x)	

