Reference: Elimite™ Cream (permethrin) 5% (Prestium Pharma, Inc.)

*Treatment compliance will be calculated based off the following criteria: 1.) all patients randomized will have at least 1 dose, confirmed from the study drug administration form via the eCRF. Date of first and last dose and total confirmed doses applied will confirm treatment use. 2.) A patient who is required to dose a second time, compliance will be calculated using criteria 1 and the following data points (via the eCRF) positive microscopic result at Visit 2 and selection of “yes” regarding the question “based on your assessment and microscopic results, is continued treatment required?”

PROGRAM: L:\DEV\755\71675502\SAS\PGM\XXXX
Created on: ddmmmyy hh:mm

OUTPUT: L:\DEV\755\71675502\SAS\OUT\XXXX
Page 1 of N

L16.2.6.1 Listing of Scabies Signs and Symptoms Rating and Microscopic Evaluation of Scabies

Treatment Group	Patient Randomization Number	Visit	Scabies Lesion Count	Are there any new lesions present?	Have all original lesions healed?	Number of scraped sites	Microscopic Examination Result	Clinical Cure	Parasitological Cure	Therapeutic Cure
Test	xxxx	1	Moderate	NA	NA	3	Positive (mites, eggs)			
		2	Mild	No	No	3	Positive (eggs)			
		3	Mild	No	Yes	NA	0	Negative	Yes	Yes
	xxxx	1	Moderate	NA	NA	3	Positive (eggs)			
		2	Mild	No	No	3	Positive (eggs)			
		3	Mild	Yes	Yes	0	Negative	No	Yes	No

Reference

Test: Permethrin Cream, 5%, (Encube Ethicals)
Reference: Elimite™ Cream (permethrin) 5% (Prestium Pharma, Inc.)

PROGRAM: L:\DEV\755\71675502\SAS\PGM\XXXX
Created on: ddmmmyy hh:mm

OUTPUT: L:\DEV\755\71675502\SAS\OUT\XXXX
Page 1 of N

L16.2.6.2 Listing of Patient Pruritus Assessment

Treatment Group	Patient Randomization Number	Visit 1	Visit 2	Visit 3 / Early Termination	No Itch Persistence
Test	xxxx	1 (Mild) 2 (Moderate)	1 (Mild) 1 (Mild)	0 (None) 1 (Mild)	Yes No

Reference

Test: Permethrin Cream, 5%, (Encube Ethicals)
Reference: Elimite™ Cream (permethrin) 5% (Prestium Pharma, Inc.)

PROGRAM: L:\DEV\755\71675502\SAS\PGM\XXXX
Created on: ddmmmyy hh:mm

OUTPUT: L:\DEV\755\71675502\SAS\OUT\XXXX
Page 1 of N

L16.2.6.3 Listing of Investigator Evaluator Initials On Scabies Signs & Symptoms Rating

Treatment Group	Patient Randomization Number	Visit 1	Visit 2	Visit 3 / Early Termination
Test	xxxx	XYZ	D-G	D-G

Reference

Test: Permethrin Cream, 5%, (Encube Ethicals)
Reference: Elimite™ Cream (permethrin) 5% (Prestium Pharma, Inc.)

PROGRAM: L:\DEV\755\71675502\SAS\PGM\XXXX

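### A patient already counted as a failure at Visit 2 can be dropped from the per-protocol analysis for missing the second dose, because the deviation proviso has no time limit

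*SAP*

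**What the plan says.** **Outcome rule.** Under SAP section 6, non-responders to the first treatment who "have new lesions or microscopic confirmation of mites, ova, or fecal matter on Day 14 ± 4 will be treated as treatment failure". That status carries over to the Day 28 comparison. Protocol 11.5 says the same. Neither attaches a condition. Protocol 8.3 gives the inclusion of Day 14 failures, as failures, as the first key revision of the PP definition.

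**Population rule.** SAP section 7 and Protocol 11.3.1 admit three kinds of patient to PP as failures "in the final analysis on Day 28 (provided they had no significant protocol deviations"). Day 14 failures are the third kind. No cut-off date is given for the deviations, and the word significant is not defined.

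**Compliance rule.** Protocol 10.4.6 calls patients "compliant with dosing if they administer 100% of the required number of doses (i.e., one or, if necessary, two doses"). The footnote to SAP listing L16.2.5.2 carries this to the second application: "A patient who is required to dose a second time, compliance will be calculated using criteria 1 and the following data points", namely positive microscopy at Visit 2 and an investigator's yes to continued treatment.

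**Shells.** T14.1.2 lists "Non-compliance with dosing requirements" as a protocol deviation. T14.1.3.1 lists "Non-compliant with dosing requirement" under exclusion from PP.

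**Decision rule.** SAP 8.2.1 tests equivalence in PP. SAP 8.2.2 requires it for the primary analysis only.

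**The concern.** Once a patient has a failure finding at Visit 2, nothing that follows can change the primary outcome. A missed second dose therefore says nothing about whether that outcome is valid, yet it can decide whether the outcome is counted. The deviation is open only to patients found positive at Visit 2. Under Protocol 10.5.2, patients who need no second application hand the tube back. The exclusion thus depends on the outcome and can remove only failures.

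Each removal raises the observed cure rate of its arm. If similar shares of failures are lost in both arms, the arm with more failures gains more and the difference shrinks toward zero. In an equivalence trial, that favours the conclusion the sponsor seeks. Blinding does not prevent this, because the exclusion follows the Visit 2 finding and not the treatment code. The three supportive analyses are labelled PP in their shells and inherit the exclusion.

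**Working it through.** **Inputs.** From SAP section 5: Reference cure 88%, Test 5 points lower (83%), 107 per group in PP, at least 90% power, about 14% non-evaluable, 250 randomized. From SAP 8.2.1: the interval is (P_T − P_R) ± 1.645·se, with se² = P_T(1−P_T)/n_T + P_R(1−P_R)/n_R, and it must lie within ±20%. Assumed: a true Test rate of 68% (a difference exactly on the margin), and x, the share of all failures removed by this route. The documents do not give x.

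**The plan's own figure.** At 83% vs 88% and n = 107, se = √[(0.1411 + 0.1056)/107] = 0.0480. With the Yates term 1/n, power = Φ[(0.15 − 1/107)/0.0480 − 1.645] + Φ[(0.25 − 1/107)/0.0480 − 1.645] − 1 = 90.0% (exact enumeration: 89.8%). Without the correction, as in SAP 8.2.1, it is 93.0% (exact: 92.9%). For enrolment, 107/0.86 = 124.4, so 125 per group and 250 in all. The sizing reproduces.

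**Equal removal in both arms.** The cure rate among patients kept is p′ = p/[1 − (1−p)x]. Expected removals are 107·(1−p)·x. The chance of declaring equivalence comes from exact enumeration of the SAP 8.2.1 rule over the joint distribution of patients kept and cures.

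| x | Test / Reference cure rate kept | Difference (points) | Expected removed, Test / Reference | Chance of declaring equivalence |
|---|---|---|---|---|
| 0 | 68.0% / 88.0% | −20.0 | 0 / 0 | 5.1% |
| 5% | 69.1% / 88.5% | −19.4 | 1.7 / 0.6 | 6.5% (6.45%) |
| 7% | 69.6% / 88.7% | −19.2 | 2.4 / 0.9 | 7.0% |
| 10% | 70.2% / 89.1% | −18.8 | 3.4 / 1.3 | 8.0% |

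At the planned 83% vs 88%, power moves from 92.9% at x = 0 to 94.2% at 7% and 94.8% at 10%.

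**Unequal removal, same true rates.**

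| Removed, Test / Reference | Chance of declaring equivalence |
|---|---|
| 10% / 0 | 11.2% |
| 0 / 10% | 3.4% |
| 10% / 20% | 5.5% |
| 5% / 15% | 4.3% |

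The direction is fixed only when the shares are similar.

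**One patient can decide a borderline result.**
- Test 81/107 (75.7%) vs Reference 94/107 (87.9%): difference −12.1 points, se = √(0.001719 + 0.000998) = 0.0521, lower limit −0.1215 − 0.0857 = −20.7%. Equivalence fails.
- Remove one Test failure, giving 81/106 (76.4%): difference −11.4 points, se = 0.0519, lower limit −0.1144 − 0.0854 = −19.98%. Equivalence passes.

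**The case against.** **The exclusion is inferred.** This stands in part. Significant is undefined, and the written PP criteria contain no dosing criterion. The link is one general row in a shell, which a missed first dose would also fill. That row sits apart from the row for major deviations, so it can be argued that the proviso does not cover a missed second dose. SAP section 9 says the shells may not reflect every aspect of the study. A reader might infer that the plan orders these patients out; it does not. Nor is it silent on intent, since Protocol 8.3 says Day 14 failures were to be included. What remains is a proviso that undercuts that intent.

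**Exposure is narrow.** This stands. The route needs positive microscopy at Visit 2 and an investigator's yes to continued treatment. Patients who fail on new lesions alone, or only at Day 28, have no second dose to miss.

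**The bias need not favour equivalence.** This stands. A reader might infer that the effect always runs one way, but heavier removal from Reference reverses it. It is also tempting to set x at the plan's 14% allowance, which would give 9.6%. That allowance covers all patients, and 107 is the number left after it. Losing 14% of cures and failures alike from 125 per arm gives 5.2%.

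**Other routes.** A reader might treat use of another scabicide as the same defect, since Protocol 10.3.3 restricts "Any other prescription/over-the-counter (OTC)/natural/herbal scabicides" and SAP section 7 requires "Did not take any prohibited medications throughout the study". It is not the same: a patient clear at Visit 2 can also use one. It shares only the feature that it cannot change a known failure's outcome. Nor do the documents show that the second dose is hard to verify. Protocol 10.4.6 provides for diary and verbal checks at Visits 2 and 3, and 10.6.13 has re-treatment tubes weighed.

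**Ordinary practice, with a sensitivity analysis in place.** Excluding dosing non-compliers from PP is usual, and the safety-population analysis in SAP 8.2.1 keeps these patients. But here the missed dose comes after the outcome is settled, and the safety-population analysis does not decide equivalence.

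**Conclusion.** The point holds as a gap in the PP definition. As written, the plan allows a microscopy-positive Visit 2 failure to leave the primary analysis for a later event that cannot alter the outcome, and a shell points that way. It does not require this, and the protocol's stated intent is to keep such patients.

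The effect is probably small. On the margin, with equal removal of 5% to 10% of failures, the chance of declaring equivalence rises from 5.1% to between 6.5% and 8.0%. These figures rest on an assumed share, an assumed true Test rate of 68%, and equal shares in both arms. With unequal shares the error can rise or fall. This is a cheap improvement: a sentence or two removes a discretionary, outcome-dependent exclusion from the analysis that decides the trial.

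**What to change.** - **SAP section 7 and Protocol 11.3.1.** For Day 14 failures, limit the proviso to deviations up to the Visit 2 assessment. State that a patient with a failure finding at Visit 2 stays in PP as a failure whatever deviation follows.
- **Shell T14.1.3.1.** Show, by arm and by reason, how many patients excluded from PP had a failure finding at Visit 2.

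**Cost.** One or two sentences in each document and one shell, settled before database lock. No new data are needed: Visit 2 findings, doses, medications and deviations are already in listings L16.2.6.1, L16.2.5.2, L16.2.4.3 and L16.2.2. The downside is that PP will hold some patients with a deviation after Visit 2, and observed cure rates will fall slightly. The re-treatment rule is not changed.
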